## Study Outline

- Study Title:** Exoskeleton Treatment of Deconditioning Due to Limited Ambulation Caused by Illness or Injury
- Sponsor:** Ekso Bionics, Inc.  
[name]  
[name]
- Study Description:** A safety and feasibility study of robotic exoskeleton training in deconditioned patients residing in a healthcare facility.
- Overall goal:** We aim to demonstrate that EksoGT™ robotic exoskeleton training can be performed safely with patients who have been hospitalized and are at risk of experiencing a further decline in their physical condition.
- Rationale:** Patients who are hospitalized for several weeks or months are at a higher risk of decline in physical condition and are also at a higher risk of rehospitalization within 30 days of discharge. A program incorporating robotic exoskeleton training may provide sufficient physical support and challenge for patients to maintain a higher level of physical condition than if they did not undergo exoskeleton training.
- Hypothesis:** Robotic exoskeleton training during hospitalization is safe and feasible.
- Design:** Single-arm safety and feasibility study.
- Participants:** Patients who fulfill the inclusion/exclusion criteria.

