- Primary Objective:** To demonstrate that a multi-day robotic gait training regimen is safe and feasible for deconditioned patients who have been admitted to a healthcare facility.

**Primary End Point:** The primary endpoint is safety defined as the number of device-related serious adverse events per Participant and overall during the study period.

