## **2. Study Objectives**

The primary objective is to demonstrate that a multi-day robotic rehabilitation regimen is safe and feasible in deconditioned patients who have been admitted to a facility.

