## **4. Study Endpoints**

The primary endpoint is safety defined as the number of device-related serious adverse events per Participant and overall during the study period.

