## **10. General Rules for Training Sessions**

1. The goal is to have Participants train in the EksoGT daily for 30-45 minutes per session, or as tolerated, ideally over the entire time of admission, but for no greater than 5 sessions.
2. It is recommended to schedule Ekso during a 45-60 minute session.
3. Patients should achieve at least 5 minutes of stable blood pressure during standing in the EksoGT prior to walking in the device.
4. Participants may use the PreGait function to perform activities in the EksoGT and walk in EksoGT both inside and outside of the trajectory, at the therapist's discretion.

To challenge Participant:

1. In Fixed Assist, lower the swing assist for each leg as appropriate.
2. In Fixed Assist, stance support may be changed from "Full" to "Flex" as appropriate.
3. In FreeGait, stance support should begin at an appropriate level. As Participant improves stance control, support may be reduced as tolerated and clinically appropriate.
4. In FreeGait, swing assist should be assessed at "neutral". If a leg is not able to complete a step, "high"/"low assistance" may be provided for more normalized stepping. If a leg is stepping far outside of the general trajectory, "high"/"low resistance" may be provided for more normalized stepping. Progress to a more symmetrical gait.
5. In FreeGait, set swing support at lower assistance or higher resistance for an appropriate clinical challenge.

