## **11. Participant Assessments**

In-person limited screening procedures are conducted to assess minimal trial inclusion. Prior to initiating physical or psychological screening evaluations, study personnel must obtain a signed informed consent. Participant screening can then proceed to ensure the individual meets inclusion/exclusion criteria.

The following information will be obtained during *screening*:

1. Demographic data including date of birth, gender, date of illness (self-reported).
2. Past and current medical history (from medical records).
3. Reason for admission to the facility (from medical records).
4. List of current medications (from medical records).
5. Weight and height (from medical records).
6. Vital signs (HR, BP, O2 sat from medical records).

7. Written documentation from the patient's physician verifying the patient is medically stable and cleared for full weight bearing locomotor training and does not have any conditions that would exclude the Participant (see Inclusion/Exclusion criteria).
8. Current practice of standing or walking, level of assistance required, assistive devices and braces used, and any associated adverse events (self-reported).
9. Range of motion for hip flexion/extension, knee flexion/extension/ ankle dorsi/plantar flexion.
10. Upper extremity MMT to include: shoulder flexion/extension/abduction and elbow extension.
11. Skin check of back, sacrum, shins, and feet (must be done at each visit).

The following data will be collected *per session*:

1. Any adverse events/complications noted following prior to training session and during present session.
2. Assessment of skin integrity of the anterior and posterior torso, anterior tibia, sacral area and bilateral feet (before and after training).
3. Vital signs (HR, BP, O2 sat collected daily).
4. Walk time.
5. Stand/Uptime.
6. Estimated seated rest time.
7. Estimated regular overground walking time (outside of EksoGT).
8. Number of steps total and in each mode of EksoGT.
9. Time spent in each EksoGT mode.

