#### **17. Statistical Methods**

This is an observational, feasibility study; therefore, statistical methods will not be employed. Data will be reported as a number (n) of adverse events and categories of patient conditions will be assembled.

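### The objective claims that a multi-day regimen is feasible, but the only endpoint is device-related SAEs and the reporting named in Section 17 includes neither a feasibility measure nor the number of sessions

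*Protocol*

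**What the plan says.** The primary objective appears twice in the Protocol. The Study Outline sets out to demonstrate that "a multi-day robotic gait training regimen is safe and feasible", and Section 2 that "a multi-day robotic rehabilitation regimen is safe and feasible in deconditioned patients". The hypothesis in the Study Outline reads "Robotic exoskeleton training during hospitalization is safe and feasible". It shares the two-part claim but does not specify a multi-day regimen.

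Section 4 contains one endpoint: "The primary endpoint is safety defined as the number of device-related serious adverse events per Participant and overall during the study period". The Study Outline gives the same one.

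Section 17 opens with "This is an observational, feasibility study; therefore, statistical methods will not be employed" and then states the output: "Data will be reported as a number (n) of adverse events and categories of patient conditions will be assembled".

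On dose, Section 8 leaves frequency and progression to the individual case. Section 10 sets a daily target of 30 to 45 minutes "or as tolerated, ideally over the entire time of admission, but for no greater than 5 sessions". No section states a minimum. Section 6 lets participation end through the participant's choice, discharge or removal by a physician.

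Session data are collected. Section 11 lists, for every session, walk time, time upright, seated rest, time in each mode and "Number of steps total and in each mode of EksoGT".

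**The concern.** The study sets out to demonstrate two things and has an endpoint for one of them. Feasibility is not defined, no endpoint is attached to it, and the reporting statement does not mention it. Section 17 even uses the feasibility label as the reason for having no statistical methods.

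The number of sessions matters for both halves of the objective. For feasibility, whether patients come back for a second and later session is the most direct evidence about a multi-day regimen. For safety, an SAE count speaks to such a regimen only to the extent that participants received one. Suppose every participant stopped after one session in one study and every participant had five in another. With the same adverse events in the same kinds of patient, both would give the output that Section 17 names, although the first would speak against a multi-day regimen.

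**Working it through.** **Text check.** The protocol gives no power, alpha or precision figure, so there is none to reproduce.

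| Element | Safety | Feasibility | Sessions delivered |
|---|---|---|---|
| Objective (Study Outline, Section 2) | yes | yes | multi-day |
| Hypothesis (Study Outline) | yes | yes | not mentioned |
| Endpoint (Section 4) | device-related SAEs | none | none |
| Data collected (Section 11) | yes | not labelled as such | yes, per session |
| Output named (Section 17) | adverse event counts | none | none |

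The gap lies in the endpoint and in the reporting, not in data collection.

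**Range of exposure.** Inputs: 40 participants (Study Outline, Sample Size) and at most 5 sessions each (Sections 8 and 10). Assume that all 40 train at least once. The protocol does not guarantee this, since a participant could consent and have no session.

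- Lowest total: 40 × 1 = 40 sessions.
- Highest total: 40 × 5 = 200 sessions.

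**What zero device-related SAEs would mean.** Zero is an illustration, not a forecast. The exact one-sided 95% upper limit with no events in N independent units is 1 − 0.05^(1/N).

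- Per participant, N = 40: 1 − 0.05^(1/40) = 7.2%, whatever number of sessions each received.
- Per session, taking sessions as independent with constant risk:

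| Mean sessions per participant | Total sessions N | Upper limit per session |
|---|---|---|
| 1 | 40 | 7.2% |
| 2 | 80 | 3.7% |
| 3 | 120 | 2.5% |
| 5 | 200 | 1.5% |

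The per-participant statement is the same in every row. The per-session statement changes almost fivefold, and the output named in Section 17 would not show which row applies.

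**Precision of a simple feasibility proportion.** Exact (Clopper-Pearson) two-sided 95% intervals with 40 participants:

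- 20 of 40 (50%): 33.8% to 66.2%
- 30 of 40 (75%): 58.8% to 87.3%
- 36 of 40 (90%): 76.3% to 97.2%

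Forty participants are therefore enough for an informative description.

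**The case against.** The strongest reply is that this is a small single-arm pilot and that tables of session data are commonly left to a statistical analysis plan, which is not at hand. Section 17 does not say that nothing else will be reported. The session data are collected, and under Section 26 monitors check that reasons for not completing are recorded. Adverse events and the conditions of the patients trained also bear indirectly on whether training can be delivered.

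Part of this stands. It would be wrong to infer that session data are missing or that they will be withheld; the documents show only that their reporting is not planned in the protocol. It would also be wrong to infer that the SAE count has no denominator, because Section 4 asks for it per participant. What does not stand is deferral of the endpoint. Endpoints belong in the protocol, Section 4 fixes one, and Section 17 refers to no further document.

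A reader might go on to infer that the study needs a formal success criterion for feasibility, or a minimum number of sessions. The documents support neither. They give no benchmark from which a threshold could be derived, and individualised dosing is a reasonable choice in a mixed inpatient population. Discharge is also an ordinary end of participation under Section 6, so a pass/fail rule that scored early discharge as failure would be hard to defend.

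The low end of the exposure range is an extreme. Section 10 aims at daily training, so a mean of one session is possible but is not what the sponsor intends.

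**Conclusion.** The point holds as a mismatch within the protocol: feasibility is claimed in the objective and the hypothesis, but it has no definition, no endpoint and no named output, and session exposure is not among the items to be reported. It should be corrected, but it does not undermine the study. The SAE count remains valid as a count and per participant.

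Its size is the range of exposure that the same output could conceal: 40 to 200 sessions if all 40 participants train, or 7.2% against 1.5% as the per-session upper limit after zero events. The per-session figures rest on independent sessions with constant risk. That is doubtful in frail patients, whose stopping may be related to their risk, so the figures illustrate what is unknown and do not estimate the hazard. The textual finding does not depend on that assumption.

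**What to change.** **Section 4.** Add a descriptive feasibility endpoint: the number and proportion of enrolled participants who train in the device on at least 2 separate days, with an exact 95% interval. Two days is the smallest dose that can be called multi-day. Use the actual number enrolled as the denominator, so that the measure still works if fewer than 40 are enrolled. State which point of enrolment is meant, because Section 5 requires eligibility as well as consent while Section 8 counts from consent alone.

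**Section 17.** Report the number of participants with 0, 1, 2, 3, 4 and 5 sessions, the total number of sessions, and the reasons for stopping (discharge, withdrawal, physician removal). Place these beside the device-related SAE count, given per participant and per session. Replace the statement that no statistical methods will be used with one that the analysis is descriptive.

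**Alternative.** If the sponsor does not want a feasibility endpoint, remove the feasibility claim from the objective and the hypothesis. Session totals should still accompany the SAE count.

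**Cost.** Wording in two sections. No new visit or measurement is needed, provided the per-session forms are dated: Section 11 already collects session data, Section 13 requires an End of Study form at discharge, and Section 26 covers reasons for not completing. The downside for the sponsor is that an unfavourable session distribution would become visible.

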## **18. Investigative Centers/Minimum and Maximum Enrollment**

Up to five centers will participate in the study. Centers are chosen based on experience with the EksoGT device and having appropriate personnel to conduct and support research studies. Each center is expected to contribute at least 8 Participants (20%) and no more than 20 Participants (50% of total).

## **19. Quality Assurance of the Data**

Participant case report forms will be collected and reviewed for completeness and accuracy by the Monitor as well as for any evidence suggesting Participant risk. Where discrepancies are noted, they will be resolved with the investigator and/or an individual designated by the investigator. Where the data set is incomplete, attempts will be made to obtain the missing data. The Sponsor reserves the right to use a third-party data manager throughout the study period. The data manager will be required to have quality assurance procedures in place.

## **20. Study Termination**

The Sponsor reserves the right to terminate the study before enrollment has been completed and to report on study results at interim time-points without statistical penalty.

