### Exclusion criteria:

1. Currently involved in another intervention study.
2. Transferred to the intensive care unit or isolation-room stay.
3. Currently on a ventilator or extracorporeal membrane oxygenation

(ECMO) machine.

4. Currently have a ventricular assist device (VAD) or an automatic implantable cardioverter-defibrillator (AICD).
5. Advanced heart failure - ejection fraction of < 20%.
6. Documented cardiovascular risk from exercise.
7. Resting heart rate <50 bpm or >120 bpm.
8. Uncontrolled or new (within 24 hours) arrhythmias.
9. Resting blood pressure below 90/70 or above 160/100.
10. Oxygen saturation (O2 sat) < 90% during rest.
11. Uncontrolled or severe orthostatic hypotension that limits standing tolerance.
12. Cardiac ischemia within 24 hours.
13. Unresolved or new (within 24 hours) deep vein thrombosis.
14. Concurrent severe neurological pathology/disease or stroke within 72 hours.
15. Open skin ulcerations on any body surfaces in contact with exoskeleton.
16. Acute fracture
17. Osteoporosis
18. Active heterotrophic ossification (HO) of the lower extremity, hip dysplasia, or hip/knee axis abnormalities.
19. Current chemotherapy
20. Inability to speak or understand the English language.
21. Inability to cooperate in tests/exercises.
22. Hip flexion contracture greater than ~17°.
23. Knee flexion contracture greater than 12°.
24. Unable to achieve neutral ankle dorsiflexion with passive stretch (neutral with max 12° knee flexion).
25. Cognitive impairments - unable to follow 2 step commands or to communicate pain or to stop session.
26. Pregnancy
27. Any reason the physician may deem as harmful to the participant to enroll or continue in the study.

- Sample Size:** Forty (40) Participants who meet the inclusion and exclusion criteria will be enrolled.
- Blinding:** Blinding will not be implemented during this study.
- Setting/Sites:** Hospital, long-term care facilities, or skilled nursing facilities (up to 5 clinical sites). Sites are to be chosen based on having Ekso Level 2 training certification, location, enrollment capabilities, and resources.
- Duration:** Each enrolled Participant is expected to engage in this study for up to 2 weeks. The duration of the study is expected to be approximately 6 months.
- Assessment periods:** The study consists of a screening period and up to 5 training sessions with assessments for safety.

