The case report form package for this study includes dedicated adverse event and serious adverse event forms. An independent Data Safety Monitoring Board (DSMB) will assess and adjudicate all SAEs and protocol violations.

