## 27. Publication

Manuscripts, abstracts, posters, or other informational materials may be presented at scientific meetings, or published in professional journals. The Sponsor reserves the right to publish the results on a smaller sample size. This study will be listed on clinical trials.gov. Therefore, results will be published per FDA requirements.

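### Sections 20 and 27 give the sponsor an unconditioned right to stop early, report at interim points and publish on fewer than 40 while it can see the safety count

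*Protocol*

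**What the plan says.** The Study Outline fixes the sample size: "Forty (40) Participants who meet the inclusion and exclusion criteria will be enrolled". Section 4 defines the only endpoint: "The primary endpoint is safety defined as the number of device-related serious adverse events per Participant and overall during the study period". Section 17 plans no inference: "This is an observational, feasibility study; therefore, statistical methods will not be employed".

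Three sponsor rights sit beside this. Section 20 has two. The first is early termination: "The Sponsor reserves the right to terminate the study before enrollment has been completed". The second is interim release, under which the sponsor may "report on study results at interim time-points without statistical penalty". Section 27 has the third: "The Sponsor reserves the right to publish the results on a smaller sample size". None comes with a trigger, a number or timing of looks, a minimum n, or a duty to label a report as interim.

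The sponsor is not kept from the accumulating data. The study has one arm, and the Study Outline says "Blinding will not be implemented during this study". Section 12 sends every SAE to the sponsor within 24 hours. Section 14 has the data manager produce reports periodically. Section 21 makes the sponsor responsible for investigating device-related events and for overseeing data review and analysis. On the monitoring board, Section 12 says "An independent Data Safety Monitoring Board (DSMB) will assess and adjudicate all SAEs and protocol violations"; no part in stopping the study or releasing results is given to it.

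**The concern.** The stated objective is to demonstrate safety and feasibility, and Section 9 says the device is being studied for a new indication. The evidence on safety is a raw count with no interval and no threshold. The party that makes the device sees that count and decides alone when to stop and when to publish. If the decision came to depend on the count, the published count would be a selected one.

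A smaller sample is also a weaker basis for the same sentence. Reported as bare counts, no events in 10 participants and no events in 40 read much alike, although they exclude very different risks.

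**Working it through.** **The plan's own figure.** The 40 has no stated rate, precision target or power behind it, so there is no calculation to reproduce. The centre limits in Section 18 agree with it: 8/40 = 20% and 20/40 = 50%.

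**Inputs.** The planned n of 40 is from the protocol. Interim sizes of 10, 20 and 30, and true risks of 1% to 10% per participant, are assumptions, because the protocol gives neither looks nor a rate. Participants are taken as independent with a common risk p of at least one device-related SAE.

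**1. What a zero excludes.** This step needs no assumed rate. With zero events the exact one-sided 95% upper bound U solves (1 − U)^n = 0.05, so U = 1 − 0.05^(1/n).

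| n | 0.05^(1/n) | U |
|---|---|---|
| 10 | 0.7411 | 25.9% |
| 20 | 0.8609 | 13.9% |
| 30 | 0.9050 | 9.5% |
| 40 | 0.9278 | 7.2% |

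**2. How often a zero is seen.** P(0 events in n) = (1 − p)^n. The last column is the chance of a clean count at 10 that would not have lasted to 40: (1 − p)^10 × [1 − (1 − p)^30].

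| Assumed p | n = 10 | n = 20 | n = 40 | Zero at 10, at least one by 40 |
|---|---|---|---|---|
| 1% | 0.904 | 0.818 | 0.669 | 0.235 |
| 2% | 0.817 | 0.668 | 0.446 | 0.371 |
| 5% | 0.599 | 0.358 | 0.129 | 0.470 |
| 10% | 0.349 | 0.122 | 0.015 | 0.334 |

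For example, at p = 5%: 0.5987 × (1 − 0.2146) = 0.470. The direction is the same for every p between 0 and 1; the size depends heavily on p.

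**3. Would quoting the bound be enough?** In 200,000 simulated studies per rate, the report with the lowest one-sided 95% upper bound was picked from looks at 10, 20, 30 and 40. At p = 15% the bound fell below the true risk in 8.4% of studies, against 4.9% when the report was fixed at 40. At p = 10% the figures were 4.2% and 1.5%. At 2% and 5% both were zero. A bound shows the imprecision, but it does not fully correct for choosing the moment; at low risks the distortion of the bound itself is nil.

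**The case against.** The strongest reply is that the Section 20 wording is not false. A penalty for interim looks ordinarily means an adjustment for multiple testing, and Section 17 plans no test. That stands: there is no alpha to inflate, and deleting the phrase alone removes no right the sponsor holds.

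A reader might also infer that the plan ties stopping to the observed count. The text does not support that: it ties stopping to nothing. Selection is possible, not planned.

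A reader might further infer that later participants could go unreported after a favourable interim report. The protocol has counterweights. Section 27 promises registry listing and publication of results as FDA requires. Section 21 requires progress, final and adverse effect reports to the IRB and sponsor. Section 12 sends all SAEs to the IRB and has an independent board adjudicate them. These limit suppression of later participants. They do not address early termination, because the truncated sample then becomes the final result and there are no later participants to report.

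It is fair to add that this is a small pilot, that flexibility suits such studies, and that an early zero published with its n supports a weaker claim for anyone who works out the bound. The protocol does not say n would be withheld, but it plans no interval either. Finally, a separate analysis plan may exist and hold interim rules. The point does not rest on their absence here; it rests on rights that the protocol itself grants without condition.

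**Conclusion.** The concern holds in a limited form. Sections 20 and 27 permit early termination, interim reporting and publication on a smaller sample at the sponsor's discretion, in an unblinded single-arm study whose only endpoint is a count that the sponsor sees as it accrues. Nothing prevents a favourable count from deciding when to stop or report. The consequence is possible selection and an imprecise zero, not type I error.

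The firm part of the size is the bound: a zero at 10 leaves risks up to 25.9% open, and a zero at 40 up to 7.2%. The probabilities of a clean count rest on assumed rates and look sizes. The contrast of 60% with 13% at a 5% risk is one point in a range that starts at 90% against 67% at a 1% risk. It would describe the gain from selection only if the sponsor always reported at 10 when the count was zero, which the protocol does not say.

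**What to change.** Amend Sections 20 and 27 as follows, with a matching change to Section 17:

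1. Delete the last three words of the Section 20 clause on interim reporting.
2. State that the primary safety report covers every participant exposed to the device, with the planned n (40), the actual n and the reason for any shortfall.
3. Label any earlier report as interim.
4. Give the exact binomial upper bound for the proportion of participants with a device-related SAE at the n reached. Section 17 needs amending, since it now excludes statistical methods.
5. State that a favourable SAE count will not be a reason to stop or publish early. Leave termination for safety concerns, whether raised by the sponsor, the investigator, the IRB or the monitoring board, and termination for accrual or operational reasons, unrestricted.

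Item 5 must be drafted with that carve-out. A rule that allowed safety stops only on the board's recommendation would bar the sponsor from acting on its own safety concern, although Section 21 makes it responsible for investigating device-related events; it would also rely on a stopping role that Section 12 does not give the board.

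The cost is protocol wording. The sponsor loses some discretion over timing, and early reports will carry a wide interval.
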